4.4 Exclusion Criteria

- 1. Female subjects that are pregnant (positive urine pregnancy test), breast-feeding, or who are of childbearing potential and not practicing a reliable method of birth control.
- Undergone facial treatments with any prohibited treatment/procedures and/or use of any other prohibited treatment/procedure within certain time periods as listed in Protocol Section 5.3.
- 3. Excisional facial surgery (such as Blepharoplasty, Face Lift, Rhinoplasty) of the face ≤ 6 months prior to study enrollment or plans for facial surgery during the study.
- 4. History of bleeding disorders.
- 5. Presence of any skin pathology or condition that could interfere with the evaluation of the treatment areas, worsen due to the proposed treatment or require interfering topical, systemic or surgical therapy.
- 6. Recent or current history of inflammatory skin disease, infection, cancerous/precancerous lesion, unhealed wound or clinically significant acne in the proposed treatment areas. Clinically significant acne is defined as a patient whom has ≥3 active inflammatory acne lesions in the treatment areas.
- 7. History of systemic granulomatous diseases active or inactive (e.g., Sarcoid, Wegeners, TB) or connective tissue diseases (e.g., lupus, dermatomyositis).
- 8. Hypertrophic acne scars, any evidence of keloid scarring in the treatment area.
- 9. Known hypersensitivity or previous allergic reaction to any of the components of the study device (including lidocaine or any amide-based anesthetic), or has a history of allergies to any bovine collagen products, including but not limited to injectable collagen, collagen implants, hemostatic sponges, and collagen-based sutures.
- 10. Undergone or be planning to undergo desensitization injections to meat products.
- 11. Unable to communicate or cooperate with the Investigator due to a language barrier (non-English speaking), poor mental development, or impaired cerebral function.
- 12. Evidence of alcohol or drug abuse (Investigator opinion), or history of poor cooperation, non-compliance with medical treatment, or unreliability.
- 13. Use of an investigational device, biologic or drug in the past 30 days, or be currently participating in an experimental drug, biologic or device trial.

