- 14. Exhibits additional physical attributes which prevent the assessment or treatment of the atrophic scars, as judged by the Investigator, such as excessive hair, traumatic or surgical scars, excessive hyperpigmentation in the treatment area, etc.
- 15. Has a condition or be in a situation that, in the Investigator's opinion, may put the subject at significant risk, may confound the study results, or may interfere significantly with the subject's participation in the study.
- 16. An employee (or a relative of an employee) of the Investigator, Sponsor or representative of the Sponsor.

5. Methods

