7.2 Procedures for Final Study Entry

A subject is considered "Enrolled" when s/he has signed the IRB-approved informed consent form (ICF) and HIPAA authorization in the presence of the Investigator or designee. The Investigator (or designee) will collect and record medical and cosmetic procedure histories, and females of childbearing potential must have pregnancy test results evaluated as negative. All subjects must also have a negative Bellafill skin test. The Investigator will assure that each subject meets the washout requirements and eligibility criteria before randomization for study treatment.

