APPENDIX 3: Skin Test Instructions for Use

bellafill SKIN TEST INSTRUCTIONS FOR USE

DESCRIPTION

Bellafill® Skin Test is an aseptically produced device composed of purified collagen gel. Each Bellafill® Skin Test consists of 3.5% bovine collagen, 2.7% phosphate buffer, 0.9% sodium chloride, 0.3% lidocaine hydrochloride, and 92.6% water for injection.

INDICATIONS

Bellafill® Skin Test is intended to be administered intradermally into the volar forearm to identify individuals who might show hypersensitivity to injectable bovine dermal collagen devices. Patients so identified are ineligible for treatment with Bellafill®.

CONTRAINDICATIONS

- Bellafill® Skin Test contains bovine collagen and is contraindicated for patients with a history of allergies to any bovine collagen products, including but not limited to collagen injectables (except to verify questionable allergy), collagen implants, hemostatic sponges, and collagen-based sutures, because these patients are likely to have hypersensitivity to the Bellafill® Skin Test.
- Bellafill® Skin Test is contraindicated for patients with severe allergies manifested by a history of anaphylaxis or history or presence of multiple severe allergies.

- Bellafill® Skin Test contains lidocaine and is contraindicated for patients with known hypersensitivity to lidocaine.
- Bellafill® Skin Test is contraindicated for patients undergoing or planning to undergo desensitization injections to meat products, as these injections can contain bovine collagen.

WARNINGS

- If the Skin Test response is positive, the patient must not be treated with Bellafill®. If the Skin Test response is equivocal, it is recommended that a second Skin Test be administered in the opposite arm and evaluated prior to the initiation of treatment.

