Prior to being administered the Bellafill® Skin Test, the patient should be provided with a copy of the Bellafill® Skin Test Results Card. The patient should be fully apprised of the purpose of and evaluation criteria for the Skin Test.

- After verifying that contraindications to the proposed Bellafill® treatment do not exist, a Bellafill® Skin Test is administered. At the time of the initial evaluation, a complete medical history should be obtained.
- The Bellafill® Skin Test syringe must be brought to room temperature before injection.
- 3. After cleansing the site, 0.1 cc Bellafill® Skin Test should be implanted intradermally into a volar forearm surface. The results of the Skin Test must be carefully evaluated for a 4-week period prior to the initiation of treatment with Bellafill®. Patients should be instructed to notify their physicians of any untoward test response observed within the 4-week period.
- Discard the syringe after administration of the Bellafill®
 Skin Test.

a. Positive Response

A positive response consists of erythema of any degree, induration, tenderness, and swelling, with or without pruritus, which can appear immediately following implantation and persists for more than 24 hours, or appears more than 24 hours following implantation.

b. Equivocal Response

An equivocal response is one in which there is no localized skin reaction, but the patient does elicit a possible systemic reaction such as a rash, arthralgia (aching joints), or myalgia (aching muscles), which occurs at any time during the 4-week observation period. If

an equivocal response is observed, a second injection in the opposite arm is required, with observation for an additional 4 weeks. Patients demonstrating a positive or equivocal response in this second test should not be treated.

TREATMENT WITH BELLAFILL® IS CONTRAINDICATED IN ANY PATIENT EXHIBITING A POSITIVE RESPONSE OR 2 EQUIVOCAL RESPONSES.

Clinical experience has shown that the importance of screening by means of the Bellafill® Skin Test cannot be overemphasized. However, a negative Skin Test does not preclude the possibility of the

HOW SUPPLIED

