APPENDIX 4: Bellafill Instructions for Use

Bellafill[®]

Instructions for Use

Caution: Federal Law restricts this device to sale by or on the order of a physician or licensed practitioner.

DESCRIPTION

Bellafill¹ is an implant composed of non-resorbable polymethylmethacrylate (PMMA) microspheres, 30 to 50 microns in diameter, suspended in a water-based carrier gel composed of 3.5% bovine collagen, 92.6% buffered, isotonic water for injection, 0.3% lidocaine hydrochloride, 2.7% phosphate buffer, and 0.9% sodium chloride.

INTENDED USE / INDICATIONS

Bellafill is indicated for the correction of nasolabial folds and moderate to severe, atrophic, distensible facial acne scars on the cheek in patients over the age of 21 years.

CONTRAINDICATIONS

- Bellafill is contraindicated for patients displaying a positive response to the required Bellafill Skin Test. Refer to the Bellafill Skin Test Instructions for Use for complete instructions for administration and evaluation of the Skin Test.
- Bellafill is contraindicated for patients with severe allergies manifested by a history of anaphylaxis or history or presence of multiple severe allergies.
- Bellafill contains lidocaine and is contraindicated for patients with known lidocaine hypersensitivity.
- Bellafill contains bovine collagen and is contraindicated for patients with a history of allergies to any bovine collagen products, including but not limited to injectable collagen, collagen implants, hemostatic sponges, and collagen-based sutures, because these patients are likely to have hypersensitivity to the bovine collagen in Bellafill
- Bellafill is contraindicated for patients undergoing or planning to undergo desensitization injections to meat products, as these injections can contain bovine collagen.
- Bellafill is contraindicated for patients with bleeding disorders.
- Bellafill is contraindicated for use in lip augmentation and injection into the vermilion or the wet mucosa of the lip.
- Bellafill should not be used in patients with known susceptibility to keloid formation or hypertrophic scarring.

_

¹ Bellafill[®] formerly known as ArteFill[®]

WARNINGS

- The safety of Bellafill when used within 6 months of collagen, botulinum toxin, or other wrinkle therapies has not been studied.

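### The eligibility criteria omit one contraindication found in both appended labels (anaphylaxis or multiple severe allergies) and narrow another in the Bellafill label (keloid or hypertrophic scarring susceptibility)

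*Combined protocol and SAP*

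**What the plan says.** Two product labels form part of the protocol as appendices. Appendix 4 (Bellafill), under Contraindications, says: "Bellafill is contraindicated for patients with severe allergies manifested by a history of anaphylaxis or history or presence of multiple severe allergies". Appendix 3 (Skin Test) says that the test too is "contraindicated for patients with severe allergies manifested by a history of anaphylaxis", and likewise names multiple severe allergies. Appendix 4 adds: "Bellafill should not be used in patients with known susceptibility to keloid formation or hypertrophic scarring". That sentence has no limit to a body site and does not require a current scar.

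The closest criteria in Section 4.4 are items 9 and 8. Item 9 begins "Known hypersensitivity or previous allergic reaction to any of the components of the study device" and goes on to lidocaine or other amide anesthetics and to bovine collagen products. Item 8 reads "Hypertrophic acne scars, any evidence of keloid scarring in the treatment area". The synopsis has the same wording for both items.

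On entry, Section 7.2 says: "The Investigator will assure that each subject meets the washout requirements and eligibility criteria before randomization for study treatment". It also requires a negative skin test. Section 6 refers the reader to the two labels in the appendices.

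**The concern.** The list used to decide who enters the trial is looser than the labels of the two products the trial administers. A person who has had anaphylaxis from a cause unrelated to collagen or local anesthetic, or who has several severe allergies of other kinds, is not caught by item 9. A known keloid former with no keloid on the face and no hypertrophic acne scar is not caught by item 8.

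The two gaps expose different subjects. The allergy gap concerns everyone, because the skin test contains bovine collagen and is placed on every subject at Screening, including those later randomized to no Bellafill. The Skin Test label reports rare anaphylactoid responses to collagen implants. A negative skin test cannot stand in for the missing exclusion, since the test is itself contraindicated in these people.

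The scarring gap concerns subjects in Track A. The Precautions in Appendix 4 describe the implant as permanent unless physically removed, and say that safety has not been studied in people with known susceptibility to keloids or hypertrophic scarring.

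**Working it through.** No calculation applies beyond a count, and the plan states no figure to reproduce. The check sets each label contraindication against the criteria in the synopsis and in Sections 4.3, 4.4 and 5.3.

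Appendix 4 (Bellafill), 8 contraindications:

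| Label contraindication | Where the protocol carries it | Status |
|---|---|---|
| Positive skin test | Inclusion 2 | Full |
| Lidocaine hypersensitivity | Exclusion 9 | Full |
| Bovine collagen allergy | Exclusion 9 | Full |
| Desensitization injections to meat products | Exclusion 10 | Full |
| Bleeding disorders | Exclusion 4 | Full |
| Anaphylaxis or multiple severe allergies | None | Absent |
| Keloid or hypertrophic scarring susceptibility | Exclusion 8 | Narrowed |
| Injection into the lip | Outside the treatment area of Section 5.1 | Not a subject-level criterion |

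Subject-level items: 8 − 1 = 7. Of these, 5 full + 1 absent + 1 narrowed = 7.

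Appendix 3 (Skin Test), 4 contraindications: bovine collagen allergy, lidocaine hypersensitivity and meat desensitization are carried (3), and anaphylaxis or multiple severe allergies is absent (1). 3 + 1 = 4. This label has no keloid item, so the narrowing concerns the Bellafill label only.

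Item 8 can be read in two ways, because its closing reference to the treatment area may govern the keloid phrase alone or both phrases. The result is the same. Either way it asks for a scar that exists now, while the label asks about susceptibility. Keloids elsewhere on the body, hypertrophic scars that did not come from acne, and a past history with nothing visible in the treatment area all pass.

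The pattern looks like an oversight. Item 9 follows the label's list of bovine collagen products very closely, items 4 and 10 match other label contraindications, and no reason is given for leaving one out or narrowing another.

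**The case against.** The strongest reply is that the labels already close the gap. Inclusion 2 and Section 7.2 require a negative skin test. Appendix 3 directs that the test be given "After verifying that contraindications to the proposed Bellafill® treatment do not exist", with a complete medical history taken at the initial evaluation. A site that follows this step would not test a contraindicated person, who could then never satisfy inclusion 2. The step refers to contraindications to Bellafill treatment, so it reaches the keloid line as well. The Bellafill directions also call for a medical history to judge whether the patient is a suitable candidate.

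In addition, exclusion 15 covers any condition that, in the Investigator's "opinion, may put the subject at significant risk", and exclusion 5 covers a skin condition that treatment could worsen.

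On the keloid half, the pivotal acne scar study followed hypertrophic scarring and keloids as events of special interest and reported none. Adverse events were similar in its 34 subjects with Fitzpatrick types V and VI. Track B receives no Bellafill.

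Much of this is fair. The protection is incomplete but not missing, and a careful site would probably exclude these people. Three things still stand against it:

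- Section 7.2 ties entry to the protocol's eligibility criteria, and no section turns label contraindications into exclusions. A site holds two unequal lists, and the one it signs off is the more permissive.
- The protocol did not leave lidocaine, collagen, meat desensitization or bleeding disorders to judgement or to the label. It wrote each one out. Relying on opinion at about 9 sites for the remaining two is inconsistent, and whether exclusion 5 covers a tendency without a lesion is open to interpretation.
- The pivotal-study results do not answer the question for known-susceptible patients, because the same label says safety in them has not been studied.

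**Conclusion.** The concern holds. One contraindication present in both labels is absent from the eligibility criteria, and one in the Bellafill label is narrowed: 2 of the 7 subject-level items in Appendix 4 and 1 of the 4 in Appendix 3. It should be corrected because it bears on subject safety, although the safeguards above reduce the practical risk.

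The conclusion rests on reading the criteria as written and on the label texts in the appendices. The documents give no frequency for either condition among likely recruits, so no rate of affected subjects is claimed. No endpoint, analysis or estimate is affected.

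**What to change.** Add two exclusions to Section 4.4 and to the synopsis, taking the wording from the labels:

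1. A history of anaphylaxis from any cause, or multiple severe allergies, past or present.
2. Known susceptibility to keloids or hypertrophic scarring, at any body site.

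State that both are checked at Screening, before the skin test is placed. Medical history is already collected at that visit (Section 10.2.1), so no new procedure is needed.

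The cost is two lines of protocol text and an updated eligibility checklist. Some further screen failures are possible. The number is assumed to be small, since the documents give nothing from which to estimate it.

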Subject and Baseline Characteristics are presented in **Table 10**.

Table 10: Subject and Baseline Characteristics

Demographic	Bellafill	Control
	(n=128)	(n=123)
Gender		
Male	11 (8.6%)	11 (8.9%)
Female	117 (91.4%)	112 (91.1%)
Age, years		
Mean	53.2	51.2
Range	28-82	29–78
Ethnicity		
Caucasian	100 (78.1%)	101 (82.1%)
Hispanic	21 (16.4%)	20 (16.3%)
Asian	1 (0.8%)	1 (0.8%)
Other ¹	6 (4.7%)	1 (0.8%)
Facial Area Treated		
Nasolabial Folds	108 (84.4%)	104 (84.6%)
Wrinkle Severity	Mean Value	Mean Value
Nasolabial Folds ²	1.74	1.45

¹"Other" ethnicities, as reported by Bellafill subjects, were Mexican/Greek/English, Italian, Hispanic/Irish, American Indian, Native American, Middle Eastern. "Other" ethnicity, as reported by a Control subject, was Persian.

Results

The mean improvement in nasolabial fold wrinkle severity, as characterized by the masked observers, for subjects from before treatment to 6 months after completion of treatment was: Bellafill -0.77 points, and Control -0.00 points. The difference was statistically significant (p = < 0.001).

Additional Analysis

At 1 month after treatment, 0.75 points (Bellafill) and 0.74 points (Control) differences from baseline for nasolabial fold wrinkle severity were recorded. At 3 months after treatment, differences of 0.81 points (Bellafill) and 0.15 points (Control) were determined for nasolabial fold. At 12 months after treatment, a nasolabial wrinkle severity difference of 0.98 points (compared to baseline) was recorded for Bellafill subjects. No assessment of nasolabial fold wrinkle severity was performed at 12 months after treatment for Control subjects.

The number of treatment sessions and volumes administered in nasolabial folds over the course of the study are displayed in **Table 11** and **12**, respectively.

²Subjects in the Bellafill treated group had a higher baseline fold severity than those in the Control group. The difference was statistically significant (p=0.039).

Table 11: Mean Number of Treatment Sessions per Product

Area	Bellafill	Control
Nasolabial Folds	2.28 (n=108)	2.18 (n=104)

Table 12: Mean Volume of Product Used per Side(Left/Right)

Tubic 121 incum voidi	per stac(Ecreatingine	
Treatment Area	Bellafill (cc)	Control (cc)
Nasolabial Folds	0.82 (n=108)	1.46 (n=104)

b) OPEN-LABEL NASOLABIAL-FOLD STUDY

This open-label, single-arm, multi-center study assessed the safety of Bellafill injections for the correction of soft-tissue defects of the face. 157 subjects were enrolled and monitored at 3, 6, and 12 months post-treatment. Approximately 80% (126/157) of subjects completed the 1-year study. The safety data collected in this study were included in **Table 1.**

c) CONTROLLED ACNE SCAR STUDY

A prospective, multi-center, randomized, double-blind, controlled trial assessing the effectiveness and safety of Bellafill for the correction of facial atrophic acne scars was conducted. A total of 147 (97 Bellafill and 50 Saline Control) subjects were enrolled and treated in the controlled phase of the study.

The primary effectiveness endpoint was a responder analysis in which the criteria for success at 6 months was defined as 50% or more of treated scars improving by 2 or more points, based on the blinded-investigator assessment utilizing the validated 4 point Acne Scar Rating Scale (ASRS). The objective was to show that Bellafill was superior to Control in treating acne scars. The ASRS (**Table 13**) is a four-point, static scale, ranging from minimal to severe, that relies on the depth of individual scars for severity assessment

Table 13: Acne Scar Rating Scale (ASRS)

Score	Description
1	Minimal – Depth up to 0.5mm. Visibility = Perceptible with tangential lighting
2	Mild – Depth >0.5mm to <1.5mm. Visibility = Moderately detectable with tangential lighting
3	Moderate – Depth = \geq 1.5mm to <2.5mm. Visibility = Easily seen with tangential lighting
4	Severe – Depth = ≥2.5mm in depth. Visibility = Substantial shadowing with tangential lighting

Subject and Baseline Characteristics are presented in Table 14.

Table 14: Subject and Baseline Characteristics

Demographic	Bellafill (n=97)	Control (n=50)	
Gender			
Male	37 (38.1%)	20 (40.0%)	
Female	60 (61.9%)	30 (60.0%)	
Age, years			
Mean	44.6	45.3	
Range	21–67	22-63	
Race			
Caucasian	70 (72.2%)	38 (76.0%)	
Black	20 (20.6%)	8 (16.0%)	
American Indian/Native Alaskan	2 (2.1%)	0 (0.0%)	
Native Hawaiian/Pacific Islander	1 (1.0)	0 (0.0%)	
Asian	4 (4.1)	4 (8.0%)	
Other	0 (0.0%)	0 (0.0%)	
Ethnicity			
Non-Hispanic	77 (79.4%)	37 (74.0%)	
Hispanic	20 (20.6%)	13 (26.0%)	

The number and severity of scars per subject are shown in **Table 15**. There were no differences between treatment groups regarding the number of qualifying scars or their severity. The median number of scars to be treated for each subject was 8.0 in each group (mean value shown below) with a median Acne Scar Rating Scale (ASRS) severity of 3.2 in each group.

Table 15: Acne Scar Characteristics at Baseline

Number and Severity of Scars		Bellafill (n=97)	Control (n=50)
Number of qualified	N	97	50
	$Mean \pm SD$	8.9 ± 4.6	8.5 ± 3.7
Mean scar severity	N	97	50
	$Mean \pm SD$	3.3 ± 0.3	3.3 ± 0.3
Average volume/subject (mL) – Total	N	97	50
	$Mean \pm SD$	1.50 ± 1.03	2.61 ± 1.80

Note: Mean \pm standard deviation.

Results

The primary effectiveness endpoint was analyzed as a responder analysis, in which the criterion for success was defined as 50% or more of treated scars on a patient improved by two or more points on the ASRS at the 6 month visit (as evaluated by a live, blinded evaluator). The observed success rate at 6 months in the Bellafill group was 56/87 (64%) and significantly higher (p=0.0005) than in the Control group 15/46 (33%).

Bellafill was found to be effective in all Fitzpatrick skin types, and for male subjects as well as female subjects.

A secondary effectiveness endpoint was a responder analysis (i.e., success was defined as 50% or more of treated scars on a patient improved by two or more points) determined via ASRS at each time point by a live, blinded evaluator. The observed success rates in unblinded assessments at 9 and 12 months for the Bellafill group were 48/78 (61.5%) and 58/82 (70.7%). See **Figure 1**.

[figure not shown]

Figure 1: Proportion (%) of Responders Assessed by the Blinded Evaluator Based on the Observed Estimate

Additional Effectiveness Analyses

In addition to assessing patient responder rates, the response rate of individual scars was also compared. In this analysis where scars with a greater-than or equal-to two-point improvement on the ASRS over baseline were considered responders, 442/789 (56.0%) of scars in the Bellafill group and 118/397 (29.7%) of scars in the Control group were judged as successes.

Bellafill injections were superior to Control treatment at all study visits after the Week 4 touch- up injection.

Independent, masked review of photographs (IPR) from the Month 6 visit by three board- certified physicians revealed a higher ASRS response rate for Bellafill than Control subjects, but these rates were lower than those determined by live, blinded evaluators.

Subjects blinded to the treatment rated the overall degree of improvement in their treated scars using a five-point, non-validated Subject Global Aesthetic Improvement Scale (SGAIS) where 5 was "much improved", 3 was "no change" and 1 was "much worse." Seventy-seven percent (77.0%) of subjects (67/87) treated with Bellafill and forty-one percent (41.3%) treated with Control (19/46) reported improvement in their global appearance at 6 months after their injection. Subjects who were treated with Bellafill continued to report improvement in their global appearance in an unblinded assessment at Month 9 (84.6%) 66/78 and at Month 12 (83.1%) 69/83.

BENEFIT / RISK CONCLUSIONS

The benefits as determined by the improvements seen on the Acne Scar Rating Scale and patient satisfaction scale as well as the risks as assessed from short-term adverse outcomes seen after injection and rare late adverse events, are sufficiently well understood for patients to make informed decisions about device use.

d.) US 5-Year Post Approval Study (PAS001-Study P521-01)

Total number of Enrolled Study Sites and Subjects, Follow-up Rate: This was an open label uncontrolled study in which 23 sites enrolled 1008 subjects with a completion rate of 87% at the end of the 5-year study. The primary objectives were to determine the incidence of granuloma formation and the incidence of adverse events at each follow-up period. The secondary objective was to determine the subject's assessment of satisfaction using a five-point scale at each follow-up visit over the 5 year time period."

The Effectiveness Endpoint was based on: Subject satisfaction using a 5-point scale, where 1 = very satisfied, 2 = satisfied, 3 = somewhat satisfied, 4 = dissatisfied and 5 = very dissatisfied.

Study Visits and Length of Follow-up: After treatment, subsequent follow-up was conducted by mail or telephone questionnaire survey at 6, 12, and 18 months, and 2, 3 and 4 years post-treatment. Subjects were seen and examined in person at 5 years post-treatment visit.

The study population is shown in **Table 16** below. The population enrolled is typical of individuals seeking correction of NLFs in current clinical practice.

Table 16: Demographic Summary

CHARACTERISTIC	N (%) N=1008
GENDER	
Male	112 (11.1%)
Female	896 (88.9%)
ETHNICITY	
Hispanic or Latino	138 (13.7%)
Not Hispanic or Latino	870 (86.3%)
RACE ¹	
White	886 (87.9%)
Black	54 (5.4%)
Asian	12 (1.2%)
American Indian/Native Alaskan	11 (1.1%)
Native Hawaiian/Pacific Islander	2 (0.2%)
Other ²	54 (5.4%)
AGE (yrs.)	
Mean	53.76
Range	22–86

¹ Subjects were permitted to report more than one race, therefore the total number of subjects exceeds the number of subjects in the study (N=1008).

Argentinian, Black / Korean, Hispanic or Latino, Hispanic- Portuguese, Indian, Iranian, Latino, Mexican, Mexican American, Portuguese, Puerto Rican, Spanish (Spain)

3. Results: Effectiveness – Subject Satisfaction

Based on subject assessment of satisfaction (using an unbalanced and unvalidated scale), patients reported satisfaction with Bellafill treatment throughout the entire study. One year after the final treatment the mean subject satisfaction rating was 1.80 (where 1= very satisfied and 2= satisfied). At 5 years after the last treatment 83% of subjects were either very satisfied or satisfied with their treatment outcome and the mean Satisfaction score was 1.70.

e) COLLAGEN IMMUNOREACTIVITY

All subjects were required to have a Skin Test prior to being considered for injection with Bellafill.

Results of the Skin Tests – In the randomized NLF study, there were no positive Skin Tests in the 128 patients first randomized to receive Bellafill treatment or the 106 Control subjects who elected to receive Bellafill injections in the crossover cohort. Of the 141 subjects who received the collagen Control Skin Test, 6 had a positive Skin Test and were excluded from the study.

Serum IgG – In the randomized NLF study, 4 Bellafill and 2 Control subjects were not treated because they displayed abnormal baseline serum IgG levels against collagen during screening. One subject in the Bellafill group transitioned from a normal IgG level before administration of the Skin Test to a value above the normal range at 1 month after treatment. This subject's IgG levels returned to the normal range by 3 months after treatment.

² 'Other' race responses include the following:

Acne Scar Study: 175 subjects received the Bellafill Skin Test. Three subjects (1.7%) demonstrated a positive Skin Test, and were excluded.

5-Year Post Approval Study: 1211 subjects received the Bellafill Skin Test. Eight subjects (0.7%) demonstrated a positive Skin Test, and were excluded.

INDIVIDUALIZATION OF TREATMENT

A complete medical history should be obtained to determine whether the patient is an appropriate candidate for treatment with Bellafill.

HOW SUPPLIED

Bellafill is an aseptic product that is required to pass a USP sterility test before release. It is supplied in a sealed tray containing individual treatment syringes with sterile needles for single patient use, packaged in a box. Each syringe contains: 20% polymethylmethacrylate microspheres and 80% bovine collagen solution containing 3.5% bovine collagen, 2.7% phosphate buffer, 0.9% sodium chloride, 0.3% lidocaine hydrochloride, and 92.6% water for injection.

The tray lid and tip of each individual syringe is sealed with a tamper evident cover. Do not use if the tamper evidence cover is broken or removed. Do Not Sterilize.

IMMUNOGENICITY TEST PROCEDURE

Four (4) weeks prior to treatment, patients will be given a 0.1cc test injection of Bellafill skin test material intradermally in the volar forearm, to determine a patient's sensitivity to the treatment material. For a complete discussion of the Bellafill Skin Test, refer to the Instructions for Use supplied with test syringes.

Test Interpretation

The patient should observe the test site daily during the 4-week test period and notify the physician immediately if any effects indicative of a positive or equivocal response are observed or if systemic effects are experienced. A Bellafill Skin Test Results Card should be provided to the patient at the time of the Skin Test to help the patient assess the test site.

Positive Response

A positive response consists of erythema of any degree, induration, tenderness, and swelling, with or without pruritus, which can appear immediately following implantation and persists for more than 24 hours or appears more than 24 hours following implantation for any length of time.

Equivocal Response

An equivocal response is one in which there is no localized skin reaction, but the patient does elicit a possible systemic reaction such as a rash, arthralgia (aching joints), or myalgia (aching muscles) that occurs at any time during the 4-week observation period. If an equivocal response is observed, a second injection in the opposite arm is required, with observation for an additional 4 weeks. Patients demonstrating a positive or equivocal response in this second test should not be treated.

DIRECTIONS FOR USE

Bellafill is indicated for the correction of nasolabial folds and moderate to severe, atrophic, distensible facial acne scars on the cheek in patients over the age of 21 years.

- 1. Prior to treatment with Bellafill, the results of the Skin Test must be carefully evaluated; the patient must not have a response to the required Bellafill Skin Test. For a complete discussion of the Bellafill Skin Test, refer to the Instructions for Use supplied with Skin Test syringes.
- 2. Prior to treatment with Bellafill, the patient should be fully informed of the indications, contraindications, warnings, precautions, treatment responses, adverse reactions, and method of administration. Patients also should be advised that supplemental touch-up treatments might be required to achieve correction.
- 3. A complete medical history should be obtained to determine whether the patient is an appropriate candidate for treatment with Bellafill.
- 4. The patient's soft-tissue contour deficiencies should be characterized with regard to etiology, distensibility, and depth of lesion. Pretreatment photographs are recommended.
- 5. Scars selected for treatment should be atrophic distensible scars.
- 6. The Bellafill syringe must be brought to room temperature before injection.
- 7. After ensuring that the patient has thoroughly washed the treatment area with soap and water, the area should be cleaned with alcohol or other antiseptic.
- 8. Bellafill is implanted through a 26 G needle. Best results with Bellafill are achieved in defects requiring deep dermal implant placement and not into the subcutaneous fat. The rate and degree of correction in the implanted area varies with patient, treatment site, and plane of implant placement. Correction should be conservative during initial treatment.
- 9. Before injecting the patient, depress the syringe plunger until Bellafill is visible at the tip of the needle.
- 10. The best cosmetic result for NLFs can be achieved by a standard linear threading technique moving the needle back and forth beneath the skin being treated and maintaining constant injection pressure while withdrawing the needle (retrograde liner threading). Injection for acne scar can use both the retrograde linear threading and serial puncture techniques. The injection pressure is correct if the implant flows slowly and evenly, without great exertion. This technique forms a support structure beneath the skin to prevent further wrinkling and/or to maintain the scar correction.
- 11. If needles become occluded or dull during a treatment session, replacement may be necessary.
- 12. Gentle massage of the skin with the fingertips may facilitate even distribution of Bellafill immediately after implant placement.

- 13. The area and the borders of Bellafill injection should be recorded on an illustration of a face for later comparison.
- 14. The physician should instruct the patient to report to him or her any evidence of adverse texture change in the surrounding treatment site. Other problems possibly associated with the use of Bellafill should be promptly brought to the attention of the physician.
- 15. The syringe and any unused material should be discarded after a single treatment visit.
- 16. Correction should be limited to no more than 100% of the skin defect during treatment. One or two touch-up implantations at intervals of at least 2 weeks may be required to achieve the desired effect. The interval at which touch-up implantations are needed depends on the nature of the defect, the amount of implant injected, the site of placement, and the dynamics at the corrected sites.

STORAGE DIRECTIONS

Bellafill should be stored at standard domestic refrigerator temperatures. **DO NOT FREEZE**.

Bellafill has an off-white appearance. In the event that the content of a syringe shows signs of separation and/or is clear (like water), do not use the syringe and notify Suneva Medical immediately. In the United States or Canada, call toll-free [contact]. Outside of the United States or Canada call +[contact].

PATIENT COUNSELING

Patients considering treatment with Bellafill should be provided with the patient labeling, which is available by contacting Suneva Medical. Patients should be told that more than one treatment session might be required to achieve the desired correction.

ORDERING

To place an order, contact Suneva Medical, Inc. In the United States or Canada, call toll-free [contact]. Outside of the United States or Canada call +[contact]. Orders may also be sent by fax to [contact] or email to [contact].

SUNEVA MEDICAL, Inc.

[name] United States of America

Toll-free Phone in the US or Canada [contact] Outside the US or Canada Phone +[contact] [contact]

[contact] www.sunevamedical.com www.bellafill.com Part Number: 7220 REV01 (Date 08/2015)
